Clinical Study Protocol

ProSpective StUdy on DEXTENZA® SafeTy And EffIcacy following coNcomitant MIGS and Cataract Surgery

The SUSTAIN Study

Compound: Sustained Release Dexamethasone,

0.4 mg

IND Number: 146602

NCT: 04200651

Study Name: Prospective Study on DEXTENZA®

Safety and Efficacy following concomitant MIGS and Cataract

Surgery

Clinical Phase: Phase IV open label prospective

Date of Issue: 10/18/2020

Primary Investigator: [name]

Sub Investigator: [name]

Site Name & Location: New York Eye Surgery Center, [name]

CLINICAL STUDY PROT	OCOL SYNOPSIS					
TITLE	Prospective Study on DEXTENZA® Safety and Efficacy following concomitant MIGS and Cataract Surgery					
SITE LOCATION(S)	New York Eye Surgery Center, [name]					
PRINCIPAL	[name]					
Investigator						
Objective(s)	To compare dexamethasone insert to topical corticosteroid use through 90 days in glaucomatous eyes undergoing MIGS and cataract surgery as measured by: visual acuity, IOP control, adverse events, control of inflammation, macular health, and patient comfort.					
STUDY DESIGN	Prospective Fellow-Eye, Randomized Open-label Interventional Study					
STUDY DURATION	Fourteen months, including enrollment period					
ESTIMATED STUDY COMPLETION DATE	February 2022					
POPULATION Sample Size: Target Population:	40 eyes Patients with cataract and glaucoma					
TREATMENT(S) Study Drug	Sustained Release Dexamethasone, 0.4 mg					
Dose/Route/Schedule:	All study eyes will receive cataract extraction, IOL placement, minimally-invasive glaucoma surgery, and a postoperative topical antibiotic prescription. 20 eyes will be randomized to receive Sustained Released Dexamethasone, 0.4 mg. 20 eyes will be prescribed a prednisolone acetate 1% regimen.					
ENDPOINT(S)						
Primary:	 Reduction in IOP at 1 and 3 months BCVA at 1 and 3 months Difference in adverse events between groups Difference in # of glaucoma meds at 3 months 					
Secondary:	 Number of patients requiring supplemental prednisolone acetate 1% eye drops Incidence of CME at 90 days as seen on OCT Difference in Ocular Comfort Index between groups at 1 month and 3 months Difference in % of patients with absence of 					

anterior chamber cells at 30 days between groups

TABLE OF CONTENTS

Clir	nical Stu	dy Protocol Synopsis	2
List	of Table	es	4
1.	Introdu	ction	5
1.1	Type	of study	5
1.2	Introd	luction	5
1.3	Ratio	nale	5
1.4	Purpo	se	6

1.1 Type of study

This is a drug study. The IND number is: 146602.

1.2 Introduction

Following cataract surgery, the standard of care for controlling ocular inflammation has historically been a topically applied anti-inflammatory eye drop regimen. Such drops utilize steroids or non-steroidal anti-inflammatory drugs, with steroid drops being more commonly prescribed (Juthani et al. 2017). Sustained-release steroid inserts, such as the FDA-approved intracanicular dexamethasone insert DEXTENZA®, have provided a "dropless" alternative to steroid eye drop regimens. DEXTENZA® was shown to be safe and effective following cataract surgery, in terms of ocular pain and anterior chamber cell clearance, in a multi-center trial (Tyson et al. 2018). However, in prior studies of DEXTENZA®, none have specifically examined the safety and efficacy of the insert in a glaucoma patient population. Furthermore, none have examined the outcomes of the insertion of DEXTENZA® following both cataract surgery and a minimally invasive glaucoma surgery (MIGS). DEXTENZA® may be of utility to glaucoma patients because it can simplify one's combined eye drops regimen. A complicated medication schedule is a significant risk factor for poor adherence to glaucoma medication instructions (Newman-Casey et al. 2015). Furthermore, given that steroid eye drops are already administered after concomitant cataract and MIGS surgery, it is highly plausible that DEXTENZA (which uses a steroid as its active ingredient) should be similar in safety. This prospective fellow-eye study will thus target glaucomatous eyes to explore the further applications of DEXTENZA®.

1.3 Rationale

Glaucoma and cataract surgery patients face an outsize postoperative burden. In addition to taking frequent anti-inflammatory eye drops, they often continue their glaucoma medications. This can cause patient confusion and nonadherence, potentially leading to poor healing, slower recovery period, and/or cystoid macular edema. DEXTENZA®, as a sustained release anti-inflammatory insert, could help preclude adherence difficulties and increase comfort by reducing eye drop load. However, glaucoma surgeons may hesitate to adopt DEXTENZA® due to concerns regarding safety with respect to elevated intraocular pressure. This prospective study will address those concerns directly, providing timely and high-quality clinical evidence comparing DEXTENZA® to standard-of-care steroid eye drops. For physicians and patients, the results of this study will prove immediately useful for therapeutic decision-making.

1.4 Purpose

The purpose of this study is to compare the safety and efficacy of sustained-release dexamethasone insert (DEXTENZA®) to steroid eye drops after glaucoma and cataract surgery.

1.5 Rationale for Study Design

This prospective study will enroll 40 eyes from a variable number of total patients. The total patient number may vary due to the enrollment of both eyes from some patients where possible. All eyes will receive concomitant cataract and MIGS surgery. Each eye will be randomized to receive either insertion at the end of the surgery or to a standard of care prednisolone acetate 1% eye drop regimen. All eyes will receive the standard of care topical ofloxacin antibiotic regimen. The experimental group will consist of the 20 eyes receiving DEXTENZA® insertion. The control group will consist of the 20 eyes placed on the prednisolone eye drop regimen.

In terms of study procedures, the majority are among cataract and MIGS preoperative, perioperative, and postoperative standards of care. Such procedures include: pachymeter, indirect ophthalmoscope, slit lamp exam, BCVA, IOP, visual field, OCT RNFL, corneal endothelial microscopy and gonioscopy. The ocular response analyzer will record corneal hysteresis data. Corneal hysteresis, as a measure of the cornea's ability to dampen in response to an external force, has been shown in multiple studies to serve as an independently valuable risk factor indicating glaucoma progression (Lam et al. 2010; Agarwal et al. 2012; Medeiros et al. 2013). To better inform the treatment of glaucoma patients during this study, the ocular response analyzer is a valid and useful tool.

In terms of primary study endpoints, change in IOP values at 1 and 3 months are crucial for quantifying glaucoma outcome differences between groups. We will use three methods to comprehensively assess IOP changes, including Goldmann applanation tonometry, CATS tonometer prism, and the automatic IOP readings provided by the ocular response analyzer. Goldmann is the current standard of care, and thus will be the primary measure. However, CATS tonometry is a valuable supplement because it utilizes a modified prism that may better account for central corneal thickness and corneal hysteresis when providing IOP measurements (McCaffertey et al. 2019). Change in number of glaucoma medications from preop to 3 months postop will be serve as an additional metric to compare glaucoma outcomes. BCVA measurements using an ETDRS chart at 4 meters will indicate whether DEXTENZA® placement in this population affects the visual acuity improvement conferred by an IOL and MIGS. Recording adverse events is necessary not only for the integrity of the study, but also for evaluating the safety of the DEXTENZA® insert for this study population.

supplementary prednisolone acetate 1% eye drops will be recorded to compare ocular inflammation between groups. Checking for absence of anterior chamber cells at 30 days will provide another measure of control of inflammation. Incidence of cystoid macular edema at three months will be used to compare macular health between groups.

In previous trials of sustained-release ocular therapeutics, authors have commented on the need to explore patient experience as an additional measure (Kindle et al. 2018). Two modalities will be used to evaluate patient experience between groups. The Ocular Comfort Index (OCI) will be used to quantify ocular comfort. The OCI is a 12-item Likert-style questionnaire designed to assess the severity of ocular surface irritation. Authors compared the OCI against the Ocular Surface Disease Index and tear-break up time (TBUT) values, and also examined changes in OCI scores after application of lubricant to dry eyes (Johnson and Murphy 2007). Statistical analysis of those three constructs support the use of the OCI to help quantify dry eye disease severity. Although participants in this study will not represent a dry eye disease population, the OCI nevertheless provides quantifiable data on general discomfort in each eye. For sustained released dexamethasone specifically, some physicians may be wary that its location in the punctum may contribute to discomfort in a way that an intracameral or intravitreal steroid would not. The OCI would address such concerns directly. From a clinical utility standpoint, the OCI is favorable due to the questionnaire's free access, an included Excel calculator for rudimentary data analysis, and the brevity of the 12-item questionnaire. Administering the OCI at 1 month postop and 3 months postop will offer insight into both the immediate and delayed changes in ocular comfort for each group.

2. STUDY OBJECTIVES

2.1 Primary Objective

To determine the effect of dexamethasone insert through 90 days as measured by -

- Visual acuity
- IOP control
- Adverse events

2.2 Secondary Objectives

To determine the effect of dexamethasone insert through 90 days as measured by –

- Control of inflammation
- Macular health
- Patient comfort.

3. STUDY DESIGN

3.1 Study Description and Duration

This prospective, open-label, single-center, randomized, fellow-eye, October 18, 2020 Page 7

investigator-initiated clinical study seeks to investigate the safety and efficacy of the dexamethasone insert in glaucoma patients after concomitant MIGS and cataract surgery. After screening a given patient for inclusion and exclusion criteria, and gaining informed consent, the patient's eligible eye will be randomized to either receive the dexamethasone insert after concomitant cataract-MIGS or to receive prednisolone acetate 1% eye drops after concomitant cataract-MIGS. For participants who enroll only a single eye, block randomization will be performed to ensure that the type of MIGS surgeries will be balanced between the two treatment groups. This stratification is necessary because it is possible that different MIGS devices can confound endpoint measurements, such as IOP control. A stratified block randomization schedule will be developed in advance by the sub-investigator through a computer program, and each assignment will be placed in opaque, sealed envelopes that will be labeled with the stratifying MIGS category. The primary investigator will only open an envelope after a patient is enrolled and the MIGS type that is suitable for the patient is determined. In the few cases where a patient enrolls both eyes, the same MIGS surgery will be performed for each eye. Under such a circumstance, simple randomization will be sufficient to determine whether the first or second eye operated on will receive the dexamethasone insert. The other eye will be placed in the prednisolone acetate 1% eye drops group.

Per enrolled eye, the study period will last for approximately 90 days after surgery, consisting of four postop follow-up visits. At Day 1, Day 7, Day 30, and Day 90, primary and secondary endpoints will be assessed alongside standard-of-care procedures. Adjusting for enrollment period, the study will last a total of approximately twelve months.

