5. STUDY SCHEDULE OF EVENTS AND VISIT DESCRIPTIONS

5.1 Schedule of Events

Study assessments and procedures are presented by visit in Table 1.

 Table 1
 Schedule of Events

Study Procedure	Screening/ Baseline	Surgica l Visit Day 0	Day 1	Day 7	Day 30	3 MTH post-op	Early Termi nation
Visit	VISIT 1	VISIT 2	VISIT 3	VISIT 4	VISIT 5	VISIT 6	
Windows for Visits	(Day -90 to - 1)		(+/- 2 days)	(+/- 2 days)	(+/- 7 days)	(+/- 14 days)	
Inclusion/Exclusion	X						
Informed Consent	X						
Demographics	X						
Medical History and Concurrent Illnesses	X						
Concomitant Medications (inc. glaucoma meds and supp. prednisolone)	X		X	X	X	X	
BCVA (ETDRS at 4m)	X		X	X	X	X	
Visual field mean deviation	X					X	
Ophthalmic Examination (dilated fundus exam)	X		X	X	X	X	
Cataract density grade (scale 1 to 4) and type	X						
Glaucoma type and severity	X						
OCT RNFL & Macula	X					X	
Intraocular Pressure (Goldmann and CATS)	X		X	X	X	X	
Corneal Endothelial Specular Microscopy	X					X	
Gonioscopy	X					X	
Ocular Response Analyzer	X					X	
Pachymeter	X						
Indirect Ophthalmoscope	X					X	
Indicate the incision type, location, and size (mm)		X					
Type of IOL(e.g. monofocal, toric, multifocal, etc.) and lens power	X	X					
Type of MIGS device	X	X					
Record any surgical complications		X					X
Subject reported AEs prior to or after surgery	X		X	X	X	X	X
Intracanalicular dexamethasone insert		X					
Ocular Comfort Index					X	X	
Anterior chamber cell count			X	X	X	X	
Anterior chamber cell flare			X	X	X	X	
Insert Visualization			X	X	X	X	
Prescribe post-operative topical therapy regimen			X				

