8.2 Primary and Secondary Endpoints

Primary Endpoints

Effect of dexamethasone insert through Day 90 as measured by -

- 1. Mean Reduction in IOP at 1 and 3 months as measured by Goldmann Applanation Tonometer and comparison between groups
- 2. Mean change in ETDRS BCVA at 1 and 3 months and comparison between groups
- 3. Difference in adverse events between the two groups
- 4. Difference in number of glaucoma medications between the wo groups at 3 months

Secondary Endpoints

Through Day 90 as measured by -

- 1. Number of patients requiring supplemental prednisolone acetate 1% eye drops
- 2. Incidence of CME at 90 days as seen on OCT

- 3. Difference in Ocular Comfort Index between the two groups at 1 month and 3 months
- 4. Difference in percentage of patients with absence of anterior chamber cells at 30 days between groups

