10.5 Confidentiality of Data

The investigator will take all appropriate measures to ensure that the anonymity of each study patient will be maintained.

The patient's and investigator's personal data will be treated in compliance with all applicable laws and regulations.

Paper files will be secured in a locked drawer accessible only to the investigator, the research assistant, and study staff. Medflow data will be stored under password protection in the servers of the New York Eye Surgery

Center. Excel spreadsheet data will be stored locally in the sub-investigator's password-protected and antivirus-secured Macbook laptop. Participant names will be coded by randomized numbers.

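### The open-label protocol provides no masked read, named reader or OCT criterion for the CME endpoint; a coded batch read of the macular scans would be a cheap improvement.

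*Combined protocol and SAP*

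**What the plan says.** Section 3.1 opens with "This prospective, open-label, single-center, randomized, fellow-eye". The same section has the sub-investigator prepare the allocation schedule, and on opening the envelopes it says: "The primary investigator will only open an envelope after a patient is enrolled".

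Section 8.2 lists secondary endpoint 2 as "Incidence of CME at 90 days as seen on OCT". Section 1.5 gives its purpose: "Incidence of cystoid macular edema at three months will be used to compare macular health between groups". No other endpoint serves the macular-health objective of section 2.2.

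The Table 1 row "OCT RNFL & Macula" is marked at screening/baseline and at 3 months, so each eye has one scan before surgery and one after. The 3-month visit in section 5.2.1 also includes the medication review and insert visualization.

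On arm size, section 1.5 says "The experimental group will consist of the 20 eyes receiving DEXTENZA® insertion" and "The control group will consist of the 20 eyes placed on the prednisolone eye drop regimen".

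Section 10.4 says that study data are kept on paper and electronically, without mentioning OCT images. Section 10.5 adds "Participant names will be coded by randomized numbers" and refers to a research assistant and study staff. Section 9 promises hypothesis tests but names no test or significance level.

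**The concern.** Treatment has to be open here, because an insert and a course of drops cannot easily be disguised from patient or surgeon. Reading an image is a separate matter. CME is judged from a scan of the macula, while the insert sits in the punctum (section 1.5), so a scan stripped of identifiers should not reveal the arm. The protocol takes care over allocation, with sealed envelopes and stratification by MIGS type, but leaves the read of this endpoint unprotected.

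Two gaps reinforce each other. With no OCT criterion, a borderline scan is a matter of judgement. With no masking, that judgement may be made by someone who knows which treatment the eye received. Any tendency to see CME more readily in one arm would pass straight into the only macular-health comparison, and nothing in the analysis could detect or correct it.

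**Working it through.** **1. Who can know the arm.** The primary investigator opens the envelopes and the sub-investigator prepares the schedule (3.1). Medication review and insert visualization take place at the same visit as the 3-month OCT (5.2.1). No step separates this information from the scan read.

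**2. Weight of one reading.** Each arm has 20 eyes (1.5), so one changed call moves that arm's rate by 1/20 = 5 percentage points.

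**3. Expected number of events.** The document gives no CME rate, so a range of 1% to 15% per eye is assumed, the same in both arms, with no dropout and eyes treated as independent. Expected events = 40 × p, and the chance of no event = (1 − p)^40.

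| Assumed p | Expected events in 40 eyes | Chance of none | Chance of 2 or fewer |
|---|---|---|---|
| 1% | 0.4 | 67% | 99% |
| 2% | 0.8 | 45% | 95% |
| 5% | 2.0 | 13% | 68% |
| 10% | 4.0 | 1.5% | 22% |
| 15% | 6.0 | 0.2% | 5% |

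**4. Effect of arm-dependent reading on the estimate.** Let the true incidence be p in both arms. Suppose a reader who knows the arm wrongly calls CME in a fraction f of unaffected control eyes and misses a fraction m of affected insert eyes. The expected rates are:

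- control: p + (1 − p)f
- insert: p(1 − m)

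With p = 5%, f = 5% and m = 25%:

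- control: 0.05 + 0.95 × 0.05 = 9.75%
- insert: 0.05 × 0.75 = 3.75%
- false difference: 6.0 percentage points

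Over p from 2% to 10%, f from 5% to 10% and m from 0 to 50%, the cases computed give false differences of 4.5 to 14.0 points. A reader leaning the other way would produce the same sizes with the opposite sign. The values of f and m are assumptions; the document gives none.

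**5. What masking does and does not remove.** If f and m are the same in both arms, the expected difference is (p1 − p2)(1 − m − f). This is zero when the true rates are equal. A real difference would still be shrunk, to 1 − 0.25 − 0.05 = 0.70 of its size at the values used above. Masking removes the arm-dependent part of the error; a fixed criterion is needed to reduce the rest.

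**6. Effect on significance.** Section 9 names no test or level, so a two-sided Fisher exact test at 0.05 is assumed. For 20 v 20 eyes:

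- 0 v 1 event: p = 1.00
- 0 v 2 events: p = 0.49
- 0 v 4 events: p = 0.106
- 0 v 5 events: p = 0.047

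Under the model in step 4, the chance of p ≤ 0.05 is 1.9% in the 5% / 5% / 25% case and about 0.7% to 14% over the cases computed. These figures are approximate, because some patients contribute one eye to each arm (3.1) and the test ignores that pairing.

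The plan has no figure to reproduce on this point: the 40 eyes are given without a rate, effect size or power.

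**The case against.** The strongest reply is that the trial is openly declared open-label, the endpoint is secondary, and no bias has been shown. All of that is true, and it limits the weight of the point. It does not remove it, because open treatment does not require open image reading.

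Several stronger readings are tempting but go beyond the document:

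- **That CME is read with the arm known.** No reader is named. What can be said is that both investigators can know the arm and nothing prevents it.
- **That stored scans and a masked reader are already in place.** Image archiving is not stated, and nobody's skill in reading OCT is described. The random numbers in section 10.5 protect names; they do not mask the arm.
- **That events will be very few.** No rate is given. The description fits assumed rates up to about 5%, and fits less well at 10% to 15%.
- **That one reclassified scan would decide significance.** The step from 0 v 4 to 0 v 5 is a selected extreme with every event in one arm. It shows the fragility of small counts, which masking does not change, and does not measure reader bias.
- **That a masked read removes the bias completely.** An investigator who has already read a scan for clinical care may recognise it, and random reading error remains.
- **That BCVA and IOP need reordering for the same reason.** Section 5.2.1 already lists both before insert visualization at each postoperative visit, and masking of these measures would be partial at best because the patient knows the treatment.

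**Conclusion.** The point stands as a cheap improvement, not as a flaw that invalidates the comparison. The only macular-health endpoint has no named reader, OCT criterion or masked read, in a trial where both investigators can know the arm. Each call is worth 5 percentage points of an arm. One or two calls could create or erase much of an observed difference, mainly by distorting the estimate and only uncommonly by producing significance. The 5-point figure follows from the stated arm size. The event counts and the 4.5 to 14.0 point range rest on assumed CME and misreading rates. Whether arm-dependent reading would actually occur cannot be known from the document.

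**What to change.** In sections 5.2.1 and 8.2:

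1. Require that baseline and 3-month macular scans be archived.
2. Have the investigators fix an OCT criterion for CME in writing before any endpoint read.
3. Have a present staff member who is not the reader export the scans under a fresh random code (not the participant number), coded by eye so that pairing in two-eye patients reveals nothing, and in shuffled order. That person holds the key.
4. Have an existing investigator, preferably one who did not do the routine clinical read of those scans, read them in one batch against the criterion, without arm, identity or clinical notes.
5. Lock the reads before the code is broken, and only then link each eye's two scans and its arm.

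Routine clinical reads stay as they are.

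The cost is relabelling and re-reading about 80 scans (40 eyes × 2). No visit, procedure or outside assessor is added, and sample size is unaffected. Masking may be imperfect if a scan is recognised, which the report should acknowledge.

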5.2 Study Visit Descriptions

5.2.1 Study Procedures

Screening/Baseline (Day -90 to-1)

After the patient has provided informed consent, the following information will be collected:

- 1. Inclusion/exclusion
- 2. Demographics
- 3. Medical history and concurrent illnesses
- 4. Concomitant medications
- 5. Best-corrected visual acuity as measured by ETDRS chart at 4m
- 6. Visual field mean deviation
- 7. Ophthalmic examination
- 8. Grade cataract density and identify type
- 9. Glaucoma type and severity
- 10. OCT RNFL & Macula
- 11. Goldmann Intraocular pressure and CATS intraocular pressure
- 12. Corneal endothelial specular microscopy
- 13. Gonioscopy
- 14. Ocular Response Analyzer
- 15. Pachymeter
- 16. Indirect ophthalmoscope
- 17. Type of IOL
- 18. Type of MIGS device (Hydrus, iStent, canaloplasty, or Kahook Dual-Blade)
- 19. Subject reported AEs prior to surgery

Surgical visit/Day 0

- 1. Indicate the incision type, location, and size
- 2. Type of IOL
- 3. Type of MIGS device (Hydrus, iStent, canaloplasty, or Kahook Dual-Blade)
- 4. Record any surgical complications
- 5. Intracanicular dexamethasone insert

Day 1 postop (+/- 2 days)

- 1. Concomitant medications
- 2. Best-corrected visual acuity as measured by ETDRS chart at 4m
- 3. Ophthalmic examination
- 4. Goldmann Intraocular pressure and CATS intraocular pressure
- 5. Subject reported AEs after surgery
- 6. Anterior chamber cell count
- 7. Anterior chamber cell flare
- 8. Insert Visualization
- 9. Prescribe post-operative topical therapy regimen

Day 7 postop (+/- 2 days)

1. Concomitant medications

October 18, 2020 Page 13

- 2. Best-corrected visual acuity as measured by ETDRS chart at 4m
- 3. Ophthalmic examination
- 4. Goldmann Intraocular pressure and CATS intraocular pressure
- 5. Subject reported AEs after surgery
- 6. Anterior chamber cell count
- 7. Anterior chamber cell flare
- 8. Insert Visualization

Day 30 postop (+/- 7 days)

- 1. Concomitant medications
- 2. Best-corrected visual acuity as measured by ETDRS chart at 4m
- 3. Ophthalmic examination
- 4. Goldmann Intraocular pressure and CATS intraocular pressure
- 5. Subject reported AEs after surgery
- 6. Anterior chamber cell count
- 7. Anterior chamber cell flare
- 8. Insert Visualization
- 9. Ocular Comfort Index

3 month postop (+/- 14 days)

- 1. Concomitant medications
- 2. Best-corrected visual acuity as measured by ETDRS chart at 4m
- 3. Ophthalmic examination

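### For single-eye participants, the allocation envelope may be opened as early as screening, up to 90 days before surgery, and nothing ties opening to the operation or locks the MIGS choice

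*Combined protocol and SAP*

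**What the plan says.** Section 3.1 describes a stratified block schedule for participants who enrol one eye. Concealment is by envelope: "each assignment will be placed in opaque, sealed envelopes that will be labeled with the stratifying MIGS category". The rule for opening is: "The primary investigator will only open an envelope after a patient is enrolled and the MIGS type that is suitable for the patient is determined". On when randomisation happens, the same section says only: "After screening a given patient for inclusion and exclusion criteria, and gaining informed consent, the patient's eligible eye will be randomized". The reason given for stratifying is that "it is possible that different MIGS devices can confound endpoint measurements, such as IOP control".

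Section 5.2.1 heads the first visit "Screening/Baseline (Day -90 to-1" and opens it with "After the patient has provided informed consent, the following information will be collected". The list that follows includes the eligibility check and, as item 18, "Type of MIGS device (Hydrus, iStent, canaloplasty, or Kahook Dual-Blade". MIGS type is listed again at the surgical visit, and Table 1 marks both visits.

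Section 1.5 says that each eye is "randomized to receive either insertion at the end of the surgery" or to the prednisolone drops. Table 1 and Section 5.2.1 put the prescribing of the topical regimen at the Day 1 visit.

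Patients who enrol both eyes follow a separate path in Section 3.1. Simple randomisation decides which eye gets the insert, the other eye gets the drops, and both eyes have the same MIGS procedure. No envelope or time of reveal is described for them.

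**The concern.** Opaque sealed envelopes protect a comparison only until they are opened. Whatever is decided after that is decided with the arm known. In this trial the operation itself lies in that interval, and it strongly shapes the results: IOP reduction, number of glaucoma medications, visual acuity and adverse events are all primary endpoints (Section 8.2).

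If the arm is known beforehand, it could play a part in four things: a change of MIGS between screening and surgery, decisions during the operation, postponement, and withdrawal before surgery. The first bears on the factor that the protocol stratifies on because it may confound IOP. The last two affect who contributes data. Section 4 carries withdrawal and replacement in its title but gives no rule for either, and Section 9 names no analysis population. An eye whose surgery is cancelled after the envelope is opened therefore has no stated handling.

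**Working it through.** The plan gives no figure to reproduce here. The check is to put the stated events in order and see when the arm may be revealed and when it is first needed.

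**Earliest permitted reveal**

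1. Condition one is enrolment. Enrolment is not defined separately, but consent and the eligibility check both take place at screening, so it can be complete at that visit.
2. Condition two is that the suitable MIGS type has been determined. MIGS type is an item of the screening visit, so this too can be met there.
3. Screening falls between Day -90 and Day -1, and surgery is Day 0. The interval from screening to surgery is therefore 0 - (-90) = 90 days at most and 0 - (-1) = 1 day at least.
4. No other sentence in Sections 1.5, 3.1 or 5 delays the opening. The mention of the end of surgery in Section 1.5 fixes when the insert is placed, not when the assignment is revealed.

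**First step that needs the arm**

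| Step | When | Differs by arm? |
|---|---|---|
| Screening measurements, planned IOL and MIGS type | Day -90 to -1 | No |
| Cataract extraction, IOL placement, MIGS | Day 0 | No |
| Insert placement | Day 0, end of surgery | Yes |
| Topical regimen prescribed | Day 1 | Yes, for the steroid drops |

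The first arm-specific step is the insert, at the end of surgery. The whole interval between the earliest permitted reveal and that step is avoidable.

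**Is the MIGS choice fixed once the envelope is open?**

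It must be determined before opening. No text says that it may not be revised afterwards, and none says what happens to the stratum if the procedure performed differs from the one on the envelope.

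**What one lost eye represents**

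With 20 eyes per arm (Section 1.5), one eye is 1/20 = 5% of an arm. This is the weight of a single case and does not predict how many would occur.

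**The case against.** The best defence is that the authors put the MIGS choice before the reveal on purpose. A reader might infer from the 90-day window that the arm can be known while the MIGS type is still undecided. The documents do not support that, because the opening rule requires the type to be determined first. What stands is narrower: the choice is not stated to be locked. That MIGS type is listed again on Day 0 adds little, since IOL type is also listed at both visits, which fits recording the plan and then what was done.

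A reader might also take it that the operating surgeon opens the envelope. Section 3.1 says the primary investigator, and no passage says that this person operates. It is plausible in a single-center, investigator-initiated study, but it is an inference, and the argument about conduct in the operating room leans on it more than the argument about postponement and withdrawal does.

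Third, the trial is open-label, so the arm becomes known in any case. That is true after treatment, but it does not make early knowledge harmless. Concealment until the operation is complete is feasible without any later masking, and the sealed envelopes show that concealment was intended.

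Fourth, no reason is evident why insert versus drops should steer an eye toward a particular MIGS, or in which direction. This is fair. It limits what can be said about size but does not close the gap in the rule.

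**Conclusion.** The point holds for single-eye participants: the opening rule permits the arm to be known up to 90 days before surgery and throughout it, with no listed step that needs it. This rests on reading enrolment as something that can be completed at screening, which the order of events in Sections 3.1 and 5.2.1 supports.

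The documents do not allow the bias to be quantified. They give no rate of MIGS changes, cancellations or postponements and no difference in IOP effect between MIGS types, so no figure in mmHg is offered.

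Two further readings should be resisted. One is that early opening would undo the stratification. A few eyes whose procedure differs from their stratum would weaken the balance on MIGS type, but analysis by randomised arm and stratum would remain possible. The other is that the envelope rule covers all 40 eyes. It is described with the single-eye schedule. For two-eye patients the gap is that no reveal procedure is given, and the second eye's arm is known once the first is assigned, whatever the rule.

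This is a cheap improvement, not a flaw that invalidates the design.

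**What to change.** In Section 3.1, for single-eye participants:

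- Before opening, write on the envelope the MIGS type and the stratum used, with date and time.
- Open the envelope only after cataract extraction, IOL placement and MIGS are complete.

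For two-eye patients, state how the assignment is held and that it is revealed at the end of the first eye's surgery. Acknowledge that the second eye's arm is then known.

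In Section 9, state that eyes are analysed by the randomised arm and stratum, including any eye whose MIGS procedure differed from its stratum.

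The cost is a few sentences of text and one logistic burden: an insert must be on hand, under the storage conditions of Section 4.2.1, for every surgery at which an envelope is opened, including those that turn out to be in the drops arm. No visit or assessment is added.
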